Aim 3. Investigate the longitudinal effects of CogSMART-PD on cognition, neuropsychiatric symptoms and quality of life / health status in individuals with PD-MCI.

Hypothesis 3: Compared with the supportive care control group, CogSMART-PD participants will demonstrate less cognitive decline, fewer neuropsychiatric symptoms, and better QoL/HS at the 6- and 12-month follow-up assessments.

Exploratory Aim 1: To examine neural changes associated with the performance on an fMRI executive function task following participation in CogSMART.

Exploratory Hypothesis 1: Compared to the non-intervention/waitlist PD participants, CogSMART completers will evidence a reduction in the dorsolateral prefrontal gyrus (due to increased cognitive efficiency) during an fMRI task of executive functioning.

Exploratory Aim 2: To investigate the feasibility and efficacy of improving visual-spatial cognition by using the Wii as an adjunct to CogSMART.

Exploratory Hypothesis 2: Compared to CogSMART (without Wii) completers, participants who use Wii as an adjunct to CogSMART (CogSMART+Wii) will demonstrate greater gains in visual spatial cognition.

Exploratory Aim 3: To investigate the feasibility and efficacy of improving visual-spatial cognition and motor skills by participating in Odoroki (computer program performing physical activity to music) as an adjunct to CogSMART.

Exploratory Hypothesis 3: Compared to CogSMART (without Odoroki) completers, participants who practice Odoroki as an adjunct to CogSMART (CogSMART+Odoroki) will demonstrate greater gains in visual spatial cognition and motor skills.

Exploratory Aim 4: To investigate changes in neuroinflammatory biomarker (cortisol, CRP, DHEA, and alpha-amylase) levels pre- and post-treatment for intervention and control participants.

Exploratory Hypothesis 4: Compared to the supportive care control group, CogSMART-PD participants will show a reduction in neuroinflammatory biomarker levels and this reduction will be associated with cognitive improvement.

Exploratory Aim 5: To investigate in the association between Brain-derived Neurotrophic Factor (BDNF) gene expression levels and cognitive change pre- to post- intervention.

Exploratory Hypothesis 5: BDNF gene expression levels will be associated with greater cognitive improvement following the CogSMART-PD intervention compared to the control condition.

Exploratory Aim 6: Investigate mediators of CogSMART-PD treatment effects.

Section 7 - Background and Significance

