Our projected sample size is consistent with the sample reported on in the preliminary data section ([name] et al., 2008). As we propose to use a similar sample size and the same cognitive rehabilitation program, we anticipate achieving similar medium to large effect sizes in the proposed study. To determine whether CogSMART will improve cognition in PD, we will employ statistical analyses including reliable change indexes to take into account change in neuropsychological test scores over the course of the intervention while also accounting for predicted practice effects. We will compare the treatment and control groups on baseline and three-month change scores. Group comparisons of differences and

changes in neuropsychological test scores between as well as within groups will also be determined via repeated measures (RM) ANCOVAs. Cognitive, functional, and quality of life indices of both participants and caregivers will be of interest in determining efficacy of treatment.

As an exploratory aim, we will recruit 60 additional individuals to complete the protocol as described above and in addition, participate in two (pre/post) hour-long brain imaging (fMRI) sessions. The imaging sessions will consist of a structural brain scanning and participation in an fMRI cognitive task (please see below). Following the baseline evaluation, half of the participants will be randomly assigned to the intervention group ($n = 30$) and participate in the CogSMART program. The groups will be broken up to consist of 8-10 individuals. The remaining participants ($n = 30$) will be assigned to the non-intervention /waitlist ("care-as-usual") group. This group will also be broken down into groups of 8-10 when enrolled in the intervention. Participants will be retested by a group assignment-blinded examiner on the clinical and cognitive battery and imaging protocol following the intervention or waitlist.

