Upon meeting study criteria, participants will be randomized to one of two 10-week conditions (CogSMART-PD or Supportive Care). Randomization will occur in blocks (i.e., first 5 people enrolled will be assigned to the intervention group, next 5 will be assigned to control group, next 5 will be assigned to the intervention group, and so on until the sample size of 55 per group is met). Within one to 1.5 weeks prior to beginning the group, participants will be tested by a research assistant blinded to group assignment on a 2-2.5 hour

battery of cognitive, neuropsychiatric, health status/QoL, and strategy use measures as well as a motor assessment (UPDRS-Part III), which will immediately precede the cognitive assessment (please see Assessment/Materials). Participants will be tested in the “on-state” of parkinsonian medications to limit confounding variability (e.g., of motor symptoms, such as tremor) on test results. All participants will be tested at the same time, preferably in the morning, if possible. Breaks will be given during the assessment as needed. Groups will consist of 5 individuals with PD-MCI and be led by a trained clinician (who is not involved in the clinical care or assessment of these participants). Following the intervention and 6- and 12-months post-intervention, PD-MCI participants will be re-tested by a group-blinded research assistant. 24 months post-intervention, participants will be asked to complete a brief (15 minute) telephone interview regarding changes in health status or living situation since the 12-month follow up. Following the 12-month follow-up, the control (support) group will be permitted to join CogSMART-PD.

Assessment/Materials: Outcome measures were carefully selected so that they: 1) represent areas that are frequently impaired, dysfunctional, or problematic for individuals with PD-MCI; 2) correspond to domains that are targeted for improvement by the CogSMART-PD intervention; 3) have adequate psychometric properties for use in PD; and 4) have shown utility and applicability based on the pilot and preliminary studies. Total neuropsychological and motor testing time is estimated to be 2-2.5 hours.

Cognitive Function and Cognitive Strategy Assessment:

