The Unified Parkinson's disease Rating Scale - Part III (UPDRS-Part III)^{75, 76} and the modified Hoehn and Yahr Rating Scale (HYRS)^{77, 78} will be used to assess level of motor impairment and disease severity. For this assessment participants go through a series of tasks designed to assess various motor characteristics such as speech, facial expression, rigidity, finger tapping, hand movements, toe tapping, freezing of gait, balance, etc. We will also use UPDRS item #13 to assess fall risk (please see Monitoring Plan below). These are standard instruments for measuring the motor symptoms and disease severity in patients with PD and have been used extensively in both research and clinical settings. VASDHS/UCSD neurologists will perform these assessments immediately prior to the cognitive assessment at the pre and 12-month follow up evaluations.

Adjunct Performance Measures:

Motor Skill Fitness measures will be carried out by a trained research assistant at the VA Medical Center

Subjects will undergo body mass index analysis at the VA Medical Center

De-identified data from these Motor Skill Fitness measures will be analyzed in the Smart Lab at UC San Diego. No participant data will be collected there.

Client Satisfaction with the intervention will be assessed at the end of the intervention with the Client Satisfaction Questionnaire (CSQ-8)⁷⁹. The CSQ-8 is an 8-item, 2-3 minute measure that yields a single score, ranging from 8 to 32 (each item rated on a 4-point Likert scale), with higher scores indicating greater satisfaction. The CSQ-8 has been widely used in clinical research trials and is reported to have excellent reliability and internal consistency, acceptability to clients and service providers, and sensitivity to different levels of program quality.

Intervention: The treatment intervention is CogSMART-PD. Participants will meet in groups of 5 individuals per group for 1.5 hours once per week for 10 weeks.

Control Group: The supportive care (control) group will entail having groups of 5 individuals with PD-MCI meet for peer-support for 1.5 hours once per week for 10 weeks. A trained clinician will serve as the facilitator of this group and will be instructed to not provide any treatment or intervention strategies. The main role of the facilitator will be to create a safe and respectful environment where members feel comfortable sharing their knowledge and insight with each other.

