Data Analysis: Preliminary analyses will begin with an examination of the distribution of variables to assess their characteristics (means, standard deviations, skewness), to provide descriptive statistics of the study population, and to allow assessment of randomization. Continuous measures will be tested for normality and homogeneity of variance. Non-normally distributed variables will be transformed to meet the normal distribution assumption for linear effects models. Analyses will include tests of randomization and comparability across conditions. Randomization will be tested by performing a series of t-tests and chi-square tests to compare the groups on demographic and initial clinical variables. Pre-specified baseline variables including age, education, gender, severity and duration of illness, and motor symptoms will be considered as potential covariates (as fixed effects) in the multivariate analyses. Any other variables (e.g., baseline cognition as assessed by the MoCA, medications) on which the groups differ initially will also be explored as covariates in subsequent analyses, as described below. In the case of missing data, appropriate data analytic techniques will be used, which may include deletion, imputation, inclusion of an indicator of missing values, or pattern-mixture modeling. Outcomes will be analyzed using SPSS release 16 (SPSS, 2007), and open source statistical software R⁸¹.

As an exploratory aim, we will recruit 60 additional individuals to complete the protocol as described above and in addition, participate in two (pre/post) hour-long brain imaging (fMRI) sessions. The imaging sessions will consist of a structural brain scanning and participation in an fMRI cognitive task (please see below). Following the baseline evaluation, half of the participants will be randomly assigned to the intervention group ($n = 30$) and participate in the CogSMART program. The groups will be broken up to consist of approximately 5 individuals. The remaining participants ($n = 30$) will be assigned to the non-intervention/control ("supportive care") group. This group will also be broken down into groups of 5 when enrolled in the intervention. Participants will be retested by a group assignment-blinded examiner on the clinical and cognitive battery and imaging protocol following the intervention or waitlist.

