Saliva samples will be labeled with participant ID numbers and date of visit only, as outlined in HIPAA authorization. Labels will not contain any other identifiable information (such as name, SSN, or date of birth). Samples will not be banked and will be destroyed after analysis.

Section 17 - Potential Benefits

17) Discuss benefits that may be gained by the subject as well as potential benefits to society in general (see ? for guidance)

Phase I:

The expected outcomes for this program include improvement in cognitive, functional performance, and quality of life of PD patients as determined by neuropsychological and functional outcome measures. It is also hypothesized that caregiver's quality of life will improve. Moreover, it is expected that participation in this program will result in fewer visits to VA or other medical services. That is, if the intervention results in prolonging of cognitive and functional independence, then the participants may utilize fewer medical resources in the long run.

Phase II:

The expected outcomes for this program include improvement in cognitive, neuropsychiatric symptoms, and quality of life in PD-MCI participants. All participants will engage in some type of treatment (cognitive rehabilitation or supportive care), therefore, all participants are expected to benefit from participation in this study. We expect that there may be improvement in mood and quality of life in the control (supportive care) group participants. However, we predict there to be greater improvements and gains in the CogSMART-PD participants, especially as it pertains to cognitive function. In addition, it is possible that participation in the intervention and/or the study overall will result in fewer visits to VA or other medical services. That is, if the intervention results in prolonging of cognitive and functional independence, then the participants may utilize fewer medical resources in the long run.

Section 18 - Risk/Benefit Analysis

18) Discuss why the risks to subjects are reasonable in relation to the anticipated benefits to subjects and in relation to the importance of the knowledge that may reasonably be expected to result.

Phase I:

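### Phase II Exploratory Hypothesis 1 keeps Phase I wording: it names a waitlist comparator where the imaging controls receive supportive care, and it limits only the treated side to completers

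*Combined protocol and SAP*

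**What the plan says.** Section 6 (Specific Aims), Phase II, Exploratory Hypothesis 1 states: "Compared to the non-intervention/waitlist PD participants, CogSMART completers will evidence a reduction in the dorsolateral prefrontal gyrus". The Phase I Exploratory Hypothesis 1 in the same section is identical.

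Section 9 (Design and Methods) describes the arms differently in the two phases:

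- **Phase I imaging.** The 30 participants outside the intervention group "will be assigned to the non-intervention /waitlist ('care-as-usual') group".
- **Phase II procedures.** On meeting criteria, "participants will be randomized to one of two 10-week conditions (CogSMART-PD or Supportive Care"). Controls may join CogSMART-PD only after the 12-month follow-up.
- **Phase II control group.** It consists of "groups of 5 individuals with PD-MCI meet for peer-support for 1.5 hours once per week for 10 weeks", with a trained clinician as facilitator.
- **Phase II imaging (under Data Analysis).** Of 60 participants, "half of the participants will be randomly assigned to the intervention group" (n = 30). The other 30 go to a control group identified as supportive care but also labelled non-intervention. The paragraph then ends with retesting on the "imaging protocol following the intervention or waitlist".

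Section 17 (Potential Benefits), Phase II, treats the control condition as more than nothing: "All participants will engage in some type of treatment (cognitive rehabilitation or supportive care").

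**The concern.** The hypothesis is the only place where the Phase II imaging contrast and its population are stated. The fMRI task and analysis text covers the task and the scanner settings but gives no group model, contrast or analysis set. An error in that one sentence is therefore not corrected downstream.

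Two things are at stake. The first is interpretation. A difference from a waitlist would include the effect of regular group contact and facilitator attention, whereas a difference from supportive care largely removes these and leaves the content of the course. A paper that follows the hypothesis wording could present the second as the first. The second is the analysis set. Completers are identified after allocation, and no matching limit is placed on controls. If that were carried into the analysis, people who stop attending would leave one arm and not the other.

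**Working it through.** The documents give no alpha, power, effect size or standard deviation for the imaging contrast, so there is no sample-size figure to reproduce. The check is a comparison of texts with two small sums.

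**1. Is there a waitlist in Phase II?** The Phase II procedures give two conditions, CogSMART-PD and supportive care. The number assigned to a waitlist is 0.

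**2. Who are the imaging controls?** The Phase II imaging paragraph splits 60 participants in half: 60 / 2 = 30 for CogSMART and 60 − 30 = 30 for supportive care. The figures agree with the text, and the two groups are concurrent.

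**3. Does the comparator label matter?** Section 9, Phase II, gives both conditions groups of 5, sessions of 1.5 hours, once a week for 10 weeks. Scheduled contact is 1.5 × 10 = 15 hours in each arm.

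| Comparator | CogSMART-PD contact | Comparator contact | Difference |
|---|---|---|---|
| Supportive care (actual) | 15 h | 15 h | 0 h |
| Waitlist with no group sessions (as named) | 15 h | 0 h | 15 h |

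The two labels therefore describe different effects.

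**4. Is the wording a carry-over?** Three features point that way. The hypothesis is word for word the Phase I one. The Phase II retest sentence still ends with a waitlist. The Phase II imaging paragraph also keeps the Phase I remark that controls will be divided into groups once enrolled in the intervention, with only the group size changed (8-10 in Phase I, 5 in Phase II). That remark fitted Phase I, where controls were offered the course after the waiting period. In Phase II, controls already meet in groups of 5 as their control condition. By contrast, Phase II Hypotheses 1 to 3 and Exploratory Hypothesis 4 all name the supportive care group.

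**5. Is the completer limit defined or balanced elsewhere?** I find no definition of completion and no parallel limit for controls. The retest sentence speaks of participants in general. The missing-data text in Data Analysis lists possible techniques without fixing an analysis set. Section 10 has a rule on data from patients whose medication changes, but it is worded for any patient and does not concern completion.

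**The case against.** The strongest reply is that the methods already settle the comparator. The Phase II imaging paragraph assigns the 30 controls to supportive care and has the participants follow the Phase II protocol. The non-intervention label in the hypothesis matches the label used there, and the facilitator is told to offer no treatment or strategies, so the label has some basis. Only the waitlist term is stray, and it might loosely refer to the later chance to join CogSMART-PD. The completer term sits in a hypothesis sentence and is not set out as an analysis rule. The aim is exploratory, and the primary comparison is unaffected.

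Most of this stands, and it limits the point. A reader might infer that the imaging contrast cannot be made at all in Phase II, or that Phase I waitlist participants are to be borrowed as controls. The documents support neither: a concurrent control group of 30 is specified, and no cross-phase comparison is proposed anywhere. A reader might also want a figure for the bias from dropping non-completers. The documents do not allow one. The Phase II Participants text reports no attrition in Phase I, and its 20% over-recruitment covers possible attrition and unusable data together, so it is not a completion rate for either arm.

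What the reply does not remove is the conflict itself. Deferred access after 12 months does not make the controls an untreated group at the post scan. And because the analysis text sets no population, the hypothesis sentence is the one an analyst would follow.

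**Conclusion.** The point holds as a low-severity correction to one exploratory aim. The stated hypothesis names a comparator that Phase II does not have and places a post-allocation limit on one side only. The 30 versus 30 comparison with supportive care remains available. What needs correcting is what the result may be said to show and who is counted.

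This rests on two readings: that the Phase II imaging paragraph, which identifies the controls as supportive care, governs over the hypothesis sentence; and that completers means those who finish the course. The size of any bias from the completer limit is unknown. It would be nil if everyone completes.

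**What to change.** 1. In Section 6, Phase II, restate Exploratory Hypothesis 1 as CogSMART-PD versus supportive care.
2. State the analysis set: all assigned participants in both arms with usable pre and post scans. This is also a subset formed after allocation, but it applies equally to both arms. Report the numbers lost, with reasons, by arm.
3. If a completer analysis is wanted, label it a sensitivity analysis and define completion beforehand, in the same way for both arms.
4. In the Phase II imaging paragraph of Section 9, replace the waitlist term in the retest sentence with supportive care. Remove the non-intervention label from the control arm, and remove the clause about controls being enrolled in the intervention. Changing the waitlist term alone would leave a non-intervention label on an arm that Section 17 counts as treatment.

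The cost is wording only: no change to numbers, scans or schedule. The claim that can be made is narrower, namely an effect relative to peer support and not relative to no intervention.

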Participants: We will recruit approximately 80 individuals who have PD and documented cognitive impairment and 80 caregivers from ongoing studies of neuropsychological functioning in PD (PI: [name]). Over-recruitment by 10% will also be instituted to account for subject attrition or unusable data and to ensure a final sample size of 20 participants (10 x 2 CogSMART groups) for Aims 1 and 2 and 60 for the Exploratory Aim. All participants will be screened and excluded if they have a history of significant head trauma, other neurologic or major psychiatric disorders, history of developmental learning disorder, substance dependence, or any contraindication to participating in the cognitive treatment. The participants' diagnosis of Parkinson's disease will be confirmed by participating neurologists and cognitive impairment (i.e., MCI or dementia) will be confirmed via neuropsychological testing and the consensus of the neuropsychologist investigators (Drs. [name] and [name]). We will also recruit any identified and consistent caregivers of the participants to complete several questionnaires regarding the participant's quality of life and daily functioning prior to and following (immediately, 3- and 9-months) the intervention. All caregivers will be asked to participate if they do not have any known memory impairment, dementia, or another condition which would prevent them from accurately completing the questionnaires.

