Approximately 240 subjects in total will be recruited for this study: 20 PD patients to participate in CogSMART only (no imaging), up to 100 PD patients to participate in CogSMART and the imaging protocol, and 120 caregivers. The PD patients will range in age from 55-95. No patients under 55 will be imaged.

One hundred twenty individuals who have PD and documented cognitive impairment will be recruited from ongoing studies of neuropsychological functioning in PD (PI [name]). Over-recruitment by 10% will also be instituted to account for subject attrition or unusable data and to ensure a final sample size of 20 participants (10 per treatment and 10 per wait list group) for Aims 1 and 2 and up to 100 participants for the Exploratory Aim. All PD participants will be screened and excluded if they have a history of significant head trauma, other neurologic or major psychiatric disorders, history of developmental learning disorder, substance dependence, or any contraindication to participating in the cognitive treatment. PD patients must be medically/clinically stable in order to be included in this study. The participant's Parkinson's disease diagnosis will be confirmed by the participating neurologists, and cognitive impairment (i.e., MCI or dementia) will be confirmed via neuropsychological testing and the consensus of the neuropsychologist investigators (Drs. [name] and [name]). We will also recruit any identified and consistent caregivers (e.g., spouse, friend, relative) of the participants to complete several questionnaires regarding the participant's quality of life and daily functioning prior to and following (immediately, 3- and 9-months) the intervention. All caregivers will be asked to participate if they do not have any known memory impairment, dementia, or another condition which would prevent them from accurately completing the questionnaires.

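### Phase I sizes Aims 1 and 2 on 20 patients and lists the 60 to 100 imaging patients only under the exploratory aim, although they supply the same three-month comparison

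*Combined protocol and SAP*

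**What the plan says.** Section 9 (Phase I, Participants) sets the total: "We will recruit approximately 80 individuals who have PD and documented cognitive impairment and 80 caregivers". It adds 10% over-recruitment to secure "a final sample size of 20 participants (10 x 2 CogSMART groups) for Aims 1 and 2 and 60 for the Exploratory Aim". Section 10 (Phase I) has the same split by aim, a "final sample size of 20 participants (10 per treatment and 10 per wait list group) for Aims 1 and 2", but puts up to 100 under the Exploratory Aim and the patient total at 120.

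Later in Section 9 (Phase I, after the analysis paragraph) the imaging cohort is described: "we will recruit 60 additional individuals to complete the protocol as described above and in addition, participate in two (pre/post) hour-long brain imaging (fMRI) sessions". Half (30) are assigned to CogSMART and half (30) to the wait-list, and "Participants will be retested by a group assignment-blinded examiner on the clinical and cognitive battery and imaging protocol following the intervention or waitlist".

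The Phase I analysis paragraph compares treatment and control on baseline and three-month change scores, with repeated-measures ANCOVA. It names no subset. The size is justified by likeness to an earlier sample: "As we propose to use a similar sample size and the same cognitive rehabilitation program, we anticipate achieving similar medium to large effect sizes". Phase I gives no significance level, power, standard deviation or numerical effect.

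**The concern.** Hypothesis 1a compares CogSMART with wait-list immediately after treatment on cognition, functional skills and quality of life. The imaging patients receive the same two conditions and the same post-treatment battery, so they inform that comparison as directly as the 20 do. The only sentences that link patients to Phase I aims nevertheless place them under the exploratory aim alone.

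If those sentences are followed, the efficacy question rests on 10 patients per arm. A null result would then be weak evidence, and a significant one would tend to overstate the effect. If they are not meant as an analysis set, Phase I has none, and whether to include the imaging cohort could be decided after the results are seen.

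The stated justification does not help. Using the same programme is a reasonable ground for expecting a similar effect, although the earlier sample was psychiatric (Section 9, Phase I). A similar sample size is no ground at all, because the size of a true effect does not depend on how many people are studied.

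**Working it through.** **The plan's own figures.** 10 x 2 = 20, and 20 + 60 = 80, which matches the approximate 80 in Section 9. Section 10: 20 + 100 = 120, which matches its 120 patients. The 20 itself cannot be derived, because no power inputs are given.

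**Share outside the efficacy aims.** 60/80 = 75% on Section 9 and 100/120 = 83% on Section 10. The 10% over-recruitment does not change these shares if it applies equally to both cohorts.

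**The two cohorts side by side (Phase I).**

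| | Non-imaging | Imaging |
|---|---|---|
| Number | 20 | 60 (Section 9; Section 11 approximately 60); 100 (Section 9.12); up to 100 (Section 10) |
| Arms | CogSMART vs wait-list, 10/10 | CogSMART vs wait-list, 30/30 |
| Allocation wording | alternation by ID number | randomly assigned after baseline |
| Assessment after treatment | clinical and cognitive battery | same battery, blinded examiner, plus fMRI |
| Patients under 55 | overall range 55-95 | none under 55 |

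The imaging age floor therefore separates nobody in Phase I. MRI eligibility does. Section 11 also sends patients who decline imaging to the non-imaging component, so the 20 may over-represent them.

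**Precision.** In standard deviation units the standard error is sqrt(2/n) for n per arm. At n = 10 it is 0.447; at n = 40 (10 + 30) it is 0.224, half as large. A stratified estimate over the cohorts gives 1/sqrt(10/2 + 30/2) = 1/sqrt(20) = 0.224, so the stratum term costs essentially nothing.

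**Illustrative power.** Two-sample t-test, two-sided 5%, non-centrality d x sqrt(n/2), 2n - 2 degrees of freedom. The plan's anticipated medium to large effect is taken as d = 0.5 to 0.8; that range and the 5% level are assumptions.

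| Per arm | d = 0.5 | d = 0.8 |
|---|---|---|
| 10 | 18.5% | 39.5% |
| 40 (20 + 60) | 59.8% | 94.2% |
| 60 (20 + 100) | 77.5% | 99.1% |

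At 10 per arm, significance needs an observed difference above 2.101 x 0.447 = 0.94 standard deviations, which is beyond the assumed large effect.

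**Baseline adjustment.** If baseline and three-month scores correlate at r = 0.5 to 0.8 (assumed), the standard error is multiplied by sqrt(1 - r^2) = 0.866 to 0.6. At 10 per arm (17 degrees of freedom), power becomes about 23 to 42% at d = 0.5 and 50 to 80% at d = 0.8. The significance threshold falls to about 0.82 to 0.57.

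**Class clustering.** With 40 treated in classes of 10 and an assumed intraclass correlation of 0.02 to 0.10, the treated-arm variance is multiplied by 1 + 9 x ICC = 1.18 to 1.90. The standard error is then sqrt((1.18 + 1)/40) = 0.233 to sqrt((1.90 + 1)/40) = 0.269. Unadjusted power falls to about 56 to 45% at d = 0.5 and 92 to 83% at d = 0.8, before any loss of degrees of freedom.

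**The case against.** The strongest reply is that exclusion is nowhere stated. The split by aim sits in a sentence about over-recruitment, which sets recruitment targets. The analysis sentence is unrestricted, and Section 5 describes imaging as something a subset also does. This stands: a reader might infer that the protocol orders the imaging data to be left out of Aims 1 and 2, and the documents do not say so. They also do not say the data are included, and the only text tying patients to aims points the other way.

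A reader might also infer that Phase II repeats the fault, because its imaging paragraph again speaks of 60 additional individuals. The documents do not support that. No Phase II sentence splits the sample by aim. Section 10 recruits 110 patients without a separate imaging cohort, and Section 9.12 says only that up to 60 may be scanned. The Phase II paragraph largely repeats the Phase I text. Whether scanned patients enter the Phase II primary analysis is an unstated detail, not a shown loss of data.

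The cohorts are not identical. Imaging patients must be MRI-eligible, their allocation is worded differently, and the scanner task shows them 24 test and 24 alternative matrix items at each session, while Matrix Reasoning is in the battery. Both imaging arms are scanned, so a common practice shift cancels between arms. A cohort term does not remove a ceiling effect or a treatment effect that differs by cohort. A cohort-by-treatment check is therefore needed, although it will be imprecise: its standard error is sqrt(2/10 + 2/30) = 0.52 standard deviations. Nor does pooling cure the alternation, which is a separate matter.

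The wait-list may take CogSMART after the three-month assessment, so the gain applies to that comparison and not to the 6- and 12-month contrasts. Finally, Section 9 (Phase II, Participants) says no attrition occurred in Phase I, which suggests that Phase I has been run. That limits what a change can now claim.

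**Conclusion.** The concern holds for Phase I, for the three-month comparison. The sample-size text ties Aims 1 and 2 to 20 patients while 60 (or up to 100) others supply comparable data. On its natural reading, 75 to 83% of those data go unused for the efficacy aims; at the least, the analysis set is undefined. Pooling 20 with 60 halves the standard error, a result that does not depend on the assumed effect but ignores clustering. The illustrative rise in power from 18-40% to 60-94% rests on an unadjusted test, two-sided 5%, d of 0.5 to 0.8 and no class effect.

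It would go too far to say that 10 per arm can show nothing: with strong baseline adjustment and a large effect, power could reach about 80%. Aim 2 carries the same ambiguity, since Section 9 plans 80 caregivers and Section 10 plans 120. The finding does not extend to Phase II.

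**What to change.** 1. In Section 9 (Phase I, Participants) and Section 10 (Phase I), state that the three-month comparison for Aims 1 and 2 uses all Phase I participants allocated to CogSMART or wait-list, imaging and non-imaging, with cohort as a stratum term. Add a cohort-by-treatment check as a sensitivity analysis. Apply the same rule to their caregivers for Aim 2. Keep the imaging cohort for the exploratory aim as well.
2. Reconcile the number imaged: 60 (Section 9; Section 11 approximately) against 100 (Section 9.12; up to 100 in Section 10), with the matching totals of 80 and 120.
3. In the Phase I sample-size paragraph, stop using similarity of sample size as a ground for expecting similar effects. The shared programme may stay as a reason, stated as an assumption.
4. State the limits beside the pooled result: MRI eligibility, matrix-type items in the scanner, and the different allocation wording (alternation against random assignment).

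The cost is text and one extra model term, with no added patients or visits. If Phase I data are already in hand, this is not a neutral wording change: the pooled analysis must be labelled post hoc.
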